10.2. Treatment Compliance

Compliance must be monitored closely and evaluated by the Investigator at each visit. Subjects will be instructed to bring all used blister cards and unused study drug with them to each visit. The number of tablets lost, if any, needs to be reported and recorded. Compliance for a study visit period will be assessed by counting the number of returned tablets, calculated by dividing the actual number of doses taken (= number of tablets dispensed – number of tablets returned – number of tablets lost per tablet count) by the number of doses the subject should have taken and multiplying by 100. All subjects will be reminded of the importance of strict compliance with taking study drug.

Subjects who miss more than 25% of scheduled doses or take more than 125% of the scheduled doses will be considered noncompliant. Evidence of noncompliance must be immediately reported to the Clinical Research Associate (CRA) and/or Medical Monitor.

10.3. Concomitant Medications and Therapies

Any medication, vaccination, or non-pharmacological therapy that is taken by or administered to the subject between signing of informed consent and final visit will be recorded in the electronic

case report form (eCRF). The entry must include the dose, frequency, route, indication, and dates of use.

Concomitant medications in the lead-in study of SEP-4199 CR that were ongoing at Visit 6/EOT (Day 42) will be entered into the eCRF for this study (SEP380-303). All changes in concomitant medications or new medications administered during the study up to the Follow-up Visit (7 ± 2 days after last dose) will be recorded.

Information on the format and version of coding dictionary is provided in the Data Management Plan (DMP). All medications will be coded using the World Health Organization drug dictionary (WHO-DD).

Ongoing treatment or initiation of treatment with non-pharmacologic psychotherapy is allowed.

10.3.1. Prohibited Medications

Treatment with other psychotropic medications (eg, antipsychotic agents, antidepressants, and mood stabilizers) is prohibited except as noted below.

The use of herbal supplements or other complementary or alternative medications during the trial is not permitted.

10.3.2. Concomitant Non-psychotropic Medications

Medications for the short-term (no more than 10 days) treatment of an acute medical condition are allowed, provided that the medications do not prolong the QTc interval. Section 23, Appendix IV provides a representative, but not exhaustive, list of medications that prolong the QT interval and are not allowed during the study. Non-psychotropic medications may be used to treat mild, chronic medical conditions. β -adrenergic antagonists used to treat stable hypertension may be continued. In addition, non-prescription pain medications (eg, aspirin, acetaminophen/paracetamol, ibuprofen) are allowed during the study provided these medications do not have a propensity for psychotropic effects and do not interfere with the evaluation of study medication. Routine vaccines (ie, seasonal influenza, pneumonia, COVID-19, etc.) are allowed based on Investigator judgement.

10.3.3. Concomitant Psychotropic Medications

Medications for treatment of movement disorders may be administered if symptoms emerge. Benztropine ($\leq 6 \text{ mg/day}$), biperiden ($\leq 16 \text{ mg/day}$), trihexyphenidyl ($\leq 15 \text{ mg/day}$), or diphenhydramine ($\leq 100 \text{ mg/day}$) are permitted as needed to treat extrapyramidal symptoms. Propranolol ($\leq 120 \text{ mg/day}$) or amantadine ($\leq 300 \text{ mg/day}$) are permitted as needed to treat akathisia.

Concomitant use of anxiolytics, sedatives, and hypnotics is permitted with the following restrictions: Lorazepam is permitted up to 2 mg/day for intolerable anxiety/agitation. Lorazepam (≤ 2 mg/day), eszopiclone (≤ 3 mg/day), zopiclone (≤ 7.5 mg/day), zolpidem (≤ 10 mg/day), zolpidem CR (≤ 12.5 mg/day), and temazepam (≤ 30 mg/day) may be administered at bedtime for insomnia, as needed. Hypnotic agents should be administered no more than once nightly and should not be used in combination.

In regions that do not have the above specified medications available, similar medications at equivalent dosages may be permitted after consultation with and approval by the Medical Monitor.

Opiates may be allowed in rare cases for a limited period of time with prior authorization from the Medical Monitor.

10.4. Contraception Requirements

Female subjects who participate in this study must be of:

- Non-childbearing potential (ie, physiologically incapable of becoming pregnant), which includes:
 - Women who have had a hysterectomy, bilateral oophorectomy, bilateral salpingectomy, bilateral tubal ligation, or bilateral tubal occlusion (as determined by subject's medical history)

OR

 Postmenopausal females, defined as at least 12 months of spontaneous amenorrhea and confirmed by follicle stimulating hormone (FSH) concentrations within postmenopausal range at Visit 1 (Screening) of the lead-in study of SEP-4199 CR as determined by the central laboratory

-OR-

- Childbearing potential with a negative urine pregnancy test at Visit 6/EOT (Day 42) of the lead-in study of SEP-4199 CR and satisfying one of the following requirements:
 - Completely abstinent from intercourse as part of the preferred and usual lifestyle of the subject. Periodic abstinence (eg, calendar, ovulation, symptothermal, postovulation methods) and the withdrawal method are not acceptable methods of contraception. Subject must have been abstinent for at least 60 days prior to administration of the first dose of study drug, throughout the Treatment Period and for a minimum of 30 days after completion or premature discontinuation from the study drug.
 - Use of effective methods of contraception during the Treatment Period and for 30 days after last dose of study drug. Effective forms of contraception include:
 - Combined (estrogen and progestogen containing) hormonal contraception associated with inhibition of ovulation (oral, intravaginal, transdermal)
 - Progestogen-only hormonal contraception associated with inhibition of ovulation (oral, injectable, implantable).
 - Implanted intrauterine device;
 - Implanted intrauterine hormone-releasing system;
 - Vasectomized partner (provided that partner is the sole sexual partner).

- Two barrier methods used in combination (eg, condom and spermicide or diaphragm with spermicide). Note: a female condom and a male condom should not be used together due to friction between the 2 barrier methods reducing effectiveness of contraception.
- Women using hormonal contraception must be supplemented with a barrier method (preferably male condom).

Post-coital methods of contraception are not permitted.

Male subjects with a female partner(s) of childbearing potential must agree to avoid fathering a child and either must be surgically sterile (with the appropriate post-vasectomy documentation of the absence of sperm in the ejaculate), completely abstinent, or use effective methods of contraception throughout the study and for at least 90 days after the last dose of study drug. Male subjects must also refrain from donation of semen/sperm throughout the study and for 90 days after last dose of the study drug. Female subjects are not allowed to donate eggs throughout the study and up to 30 days after the last dose of study drug.

10.5. Guidance for Overdose

The effects of an overdose of SEP-4199 are unknown and there is no known treatment in case of overdose. Standard symptom support measures should be used in the case of excessive pharmacological effects or overdose.

11. STUDY ASSESSMENTS

A study schematic is presented in Figure 1. A summary of assessments to be conducted at each visit is presented in Table 2.

11.1. Duplicate Subject Check

The Verified Clinical Trials LLC ("VCT") Research Subject Database ("VCT Registry") is used at study sites to help determine whether a subject is already participating in or has recently participated in another clinical trial. Subjects will be given detailed information about the processing of their personal data through the VCT Registry in a separate patient information and consent form (Verified Clinical Trials LLC Research Subject Database Declaration of Consent for the Processing of Personal Data) during the lead-in study of SEP-4199 CR and will be asked to give explicit consent by signing this separate patient information and consent form to continue to be monitored while participating in SEP380-303, where allowed under local laws and regulations. No personal data will be entered into or processed through the VCT Registry unless the relevant subject has given explicit consent.

11.2. Demographics and Baseline Characteristics

Demographics (date of birth, age, sex, ethnicity, race) and medical and psychiatric history collected in the lead-in study of SEP-4199 CR will be utilized for this study. Date of birth, age, and sex will be re-entered into the eCRF of this study.

11.3. Effectiveness Assessments

For all efficacy assessments, the open-label Baseline values are carried over from Visit 6/EOT (Day 42) assessments collected in the lead-in study of SEP-4199 CR.

11.3.1. Montgomery-Asberg Depression Rating Scale (MADRS)

The MADRS is a clinician-rated assessment of the subject's level of depression. The MADRS consists of 10 items that measure Apparent Sadness, Reported Sadness, Inner Tension, Reduced Sleep, Reduced Appetite, Difficulty Concentrating, Lassitude, Inability to Feel, Pessimistic Thoughts, and Suicidal Thoughts. Each item is scored from 0 to 6, with higher scores indicating greater symptom severity.

The MADRS will be administered by a trained and qualified rater. The MADRS interviews will be audio recorded and the recording will be reviewed by the Sponsor's designee to monitor the quality of the rater interviews, where allowed by local/regional regulations. No identifying information should be collected with the audio recording. Further information regarding administration of the MADRS, including rater training and certification as well as recording of MADRS scores, will be provided in the Study Reference Manual.

11.3.2. Clinician Global Impression-Bipolar Version-Severity of Illness (CGI-BP-S)

The CGI-BP-S is a clinician-rated assessment of the subject's current illness state on a 7-point scale, where a higher score is associated with greater illness severity. Following a clinical interview, the CGI-BP-S can be completed in 1-2 minutes. The CGI-BP-S will be completed by a qualified rater at the site.

Further information regarding administration of the CGI-BP-S, including rater training and certification as well as recording of CGI-BP-S scores, will be provided in the Study Reference Manual.

11.3.3. Hamilton Anxiety Rating Scale (HAM-A)

The HAM-A is a clinician-administered scale that was developed to quantify the severity of anxiety symptomatology. It consists of 14 items, each defined by a series of symptoms. Each item is rated on a 5-point (0-4) scale, with higher scores indicating greater severity. The Structured Interview Guide for the HAM-A (SIGH-A) will be used for administration of the HAM-A.

Further information regarding administration of the HAM-A, including rater training and certification as well as recording of HAM-A scores will be provided in the Study Reference Manual.

11.3.4. Quick Inventory of Depressive Symptomatology – Self Report (QIDS-SR16)

The QIDS-SR16 is a 16-item subject-reported depression symptom severity questionnaire. The scoring of the QIDS-SR16 converts responses to 16 separate items into the 9 DSM-IV symptom criterion domains. The total score ranges from 0-27 with higher scores indicating greater severity. The 9 domains are: sad mood, concentration, self-criticism, suicidal ideation, interest, energy/fatigue, sleep disturbance (early/middle/late insomnia or hypersomnia), decrease/increase in appetite/weight, and psychomotor agitation/retardation.

Site staff will assist the subject in the initiation of the QIDS-SR16 assessment. Clinical staff will not participate in the administration of the QIDS-SR16 after initiation. Further information regarding administration of the QIDS-SR16, including recording of scores, will be provided in the Study Reference Manual.

11.3.5. Sheehan Disability Scale (SDS)

The SDS is a subject-reported assessment of function. The SDS is a composite of 3 items designed to measure the extent to which 3 major sectors in a patient's life are impaired by depressive symptoms. This anchored visual analogue scale uses spatiovisual, numeric, and verbal descriptive anchors simultaneously to assess disability across 3 domains: work, social life or leisure activities, and home life or family responsibilities. The subject will rate his or her degree of impairment in each of these domains using an 11-point scale ranging from 0-10, with higher scores indicating more impairment. There are verbal descriptors for the points on the scale as well as numerical scores that provide more precise levels of the verbal descriptors. Scores for the 3 items are summed into a single dimensional measure of global functional impairment that ranges from 0 (unimpaired) to 30 (highly impaired).

Further information regarding administration of the SDS, including rater training and certification as well as recording of SDS scores, will be provided in the Study Reference Manual.

11.3.6. EuroQol - 5 Dimension - 5 Level (EQ-5D-5L)

The EQ-5D-5L is a subject self-reported, standardized instrument developed by the EuroQol Group as a measure of health-related quality of life that can be used in a wide range of health

conditions and treatments. The EQ-5D-5L consists of a descriptive system and the EuroQol Visual Analogue Scale (EQ-VAS).

The descriptive system includes 5 dimensions: mobility, self-care, usual activities, pain/discomfort, and anxiety/depression. Each dimension has 5 levels: no problems, slight problems, moderate problems, severe problems, and extreme problems. The subject is asked to indicate his/her health state by ticking the box next to the most appropriate statement in each of the 5 dimensions. This decision results in a 1-digit number that expresses the level selected for that dimension. The digits for the five dimensions can be combined into a 5-digit number that describes the subject's health state.

The EQ-VAS records the subject's self-rated health on a vertical visual analogue scale, where the endpoints are labeled "the best health you can imagine" and "the worst health you can imagine". The VAS can be used as a quantitative measure of health outcome that reflects the subject's own judgment.

11.3.7. Snaith-Hamilton Pleasure Scale (SHAPS)

The SHAPS (Snaith 1995) is a subject-reported questionnaire having a 14-item scale that assesses 4 domains of hedonic experience: interest/pastimes, social interaction, sensory experience, and food/drink. Subjects are asked to respond based on their ability to experience pleasure in the past few days. Each of the 14 questions is in the form of the statement "I would enjoy_____" and asks the subject to choose between the choices: strongly disagree, disagree, agree, or strongly agree.

11.4. Safety Assessments

11.4.1. Adverse Events

Adverse events will be collected for each subject. Subjects should be queried in a non-leading manner, without specific prompting (eg, "Has there been any change in your health status since your last visit?"). See Section 12, Safety Reporting. AEs and SAEs will be monitored throughout the study at all visits.

Adverse events in the lead-in study of SEP-4199 CR that were ongoing at Visit 6/EOT (Day 42) will be entered into the eCRF for this study (SEP380-303). All changes in adverse events or new adverse events occurring during the study up to the Follow-up Visit will be recorded.

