12. SAFETY REPORTING

12.1. Definitions

12.1.1. Adverse Events

An adverse event (AE) is any untoward medical occurrence associated with the use of a drug in humans, whether or not considered drug related.

Untoward medical occurrences that occur after signing Study SEP380-303 ICF will be considered AEs.

An AE can, therefore, be any unfavorable and unintended sign (including an abnormal laboratory finding), symptom, or disease occurring after the administration of a medicinal (investigational) product, whether or not considered related to the medicinal (investigational) product. AEs may include the onset of new illness and the exacerbation of pre-existing conditions. AEs will be collected from the signing of the ICF to the last study visit (Follow-up Visit).

The Investigator should attempt to establish a diagnosis of the event based on signs, symptoms, and/or other clinical information. In such cases, the diagnosis should be documented as the AE and not the individual signs/symptoms.

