12.3. Collection and Recording of Adverse Events

All AEs must be recorded in the subject's study records/source documents in accordance with the Investigator's normal clinical practice. All AEs that occur from the signing of the informed consent to the subject's last visit must be recorded on the eCRF.

All AEs will be followed until resolution, stabilization of the condition, the event is otherwise explained, or the subject is lost to follow-up.

Each AE is to be evaluated for duration, severity, frequency, seriousness, action taken with the study treatment, outcome, and causal relationship to the study treatment. Definitions for severity, frequency, action taken with the study treatment, outcome, and causal relationship to the study treatment are presented below.

The severity of AE:

- **Mild** Ordinarily transient symptoms that do not influence performance of subject's daily activities. Other treatment is not ordinarily indicated.
- **Moderate** Marked symptoms sufficient to make the subject uncomfortable. Moderate influence on performance of subject's daily activities. Other treatment may be necessary.
- Severe Symptoms cause considerable discomfort. Substantial influence on subject's daily activities. May be unable to continue the study, and other treatment may be necessary.

The frequency of AE:

- **Once** an isolated episode
- Intermittent occurs on two or more separate occasions
- **Continuous** does not abate from date of onset to date of resolution

The action taken with the study treatment:

- **Drug Interrupted** Study drug stopped temporarily.
- Drug Withdrawn Study drug stopped permanently.
- Dose Reduced
- Dose Increased
- Dose Not Changed
- Not Applicable
- Unknown

The outcome of the AE:

- Recovered/Resolved
- Recovering/Resolving
- Not Recovered/Not Resolved
- Recovered/Resolved with Sequelae
- Fatal
- Unknown

The causal relationship of the AE to the study treatment: Not related

- **Not related -** Improbable temporal relationship and is plausibly related to other drugs or underlying disease.
- Related
 - **Possible** occurred in a reasonable time after study drug administration, but could be related to concurrent drugs or underlying disease.
 - **Probable** occurred in a reasonable time after study drug administration, is unlikely to be attributable to concurrent drugs or underlying disease, and there is a plausible mechanism to implicate the study drug.

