### 18.1. ADVERSE EVENTS

Adverse Events (AEs) and pre-treatment events will be coded using MedDRA central coding dictionary, Version 22.0.

The concept of “pre-treatment events” only applies to study SEP380-301. Pre-treatment events are untoward medical occurrences that started prior to the first dose of study medication in SEP380-301.

Adverse events of study SEP380-301 are untoward medical occurrences that started at the same time of or after the first dose of study medication in SEP380-301, but before the first dose of OLE study medication in SEP380-303. These events will be recorded in the SEP380-301 databases.

Adverse events (AEs) of the SEP380-303 extension study are untoward medical occurrences that started at the same time of or after the first dose of the OLE study drug. These events will be recorded in the SEP380-303 database.

AEs (and pre-treatment events) that started in study SEP380-301 and are ongoing at the time of subject rollover will be re-entered into the SEP380-303 database and continue to be followed. These events will not be included in any AE summary table of SEP380-303. They will only be listed in a separate data listing.

Whenever available, the time information should be accounted for to determine if a record in the SEP380-303 AE database belongs to study SEP380-301 or SEP380-303. In the case where time is not available, untoward medical occurrences that started prior to the day of the first OLE dose will be considered to belong to study SEP380-301; those that started after the day of the first OLE dose will be considered to belong to study SEP380-303. Events that started on the same day of the first OLE dose will be assigned to study SEP380-301 or SEP380-303 depending on whether this AE record also exists in the SEP380-301 database (based on a comparison of subject ID, verbatim term, AE start date (and time if available), severity, and seriousness).

See [APPENDIX 2](#) for handling of partial dates for AEs.

Overall summary of the incidence of all AEs, study medication-related AEs, severe AEs, serious AEs, AEs leading to discontinuation from study, AEs leading to death, and AEs of special interest (AESI) will be provided by the actual treatment groups.

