### ALGORITHM FOR ADVERSE EVENTS

The algorithm below applies to all SEP380-301/303 AEs and SEP380-301 pre-treatment event records collected in the SEP380-303 clinical database.

Step 1) For events that exist in the SEP380-301 databases and have a missing or partial start date, retrieve imputed event start dates from the respective ADaM dataset.

Events in the SEP380-303 database which also exist in the SEP380-301 databases will be identified based on a comparison of subject ID, PT, AE start date (and time if available), severity, and seriousness.

Step 2) For events that do not exist in the SEP380-301 databases yet the known part of the event start and/or end dates show that the event unambiguously started before first OLE dose in SEP380-303, impute missing or partial event start and/or end dates (if not ongoing) using the algorithm below.

If an event has some missing components in both the start and end dates, first impute the end date.

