#### **AE start date imputation**

- If year and month (YYYY-MM) of AE start date are known and YYYY-MM = year and month of OLE study med start date, then impute AE start date to be the earlier of (OLE study med start date; full or imputed AE end date [if non-missing]).
- If year and month (YYYY-MM) of AE start date are known and YYYY-MM ≠ year and month of OLE study med start date, then impute AE start date to be YYYY-MM-01.
- If only year (YYYY) of AE start date is known and YYYY = year of OLE study med start date, then impute AE start date to be the earlier of (OLE study med start date; full or imputed AE end date [if non-missing]).
- If only year (YYYY) of AE start date is known and YYYY ≠ year of OLE study med start date, then impute AE start date to be YYYY-01-01.
- If AE start date is completely missing, then impute AE start date to be the earlier of (OLE study med start date; full or imputed AE end date [if non-missing]).

Step 4) Using the full or imputed event dates, assign events into SEP380-301 pre-treatment event, SEP380-301 AE, or SEP380-303 AE as described below.

If both event start date/time and SEP380-303 OLE study med start date/time are available:

- If event start date/time < SEP380-303 OLE study med start date/time, then SEP380-301 pre-treatment event or SEP380-301 AE\*.
- If event start date/time ≥ SEP380-303 OLE study med start date/time, then SEP380-303 AE.

If (event start date is available and time is not available) and/or (SEP380-303 OLE study med start date is available and time is not available):

- If event start date < SEP380-303 OLE study med start date, then SEP380-301 pre-treatment event or SEP380-301 AE\*.
- If event start date > SEP380-303 OLE study med start date, then SEP380-303 AE.
- If event start date = SEP380-303 OLE study med start date and the event record exists in SEP380-301 database§, then SEP380-301 pre-treatment event or SEP380-301 AE\*.
- If event start date = SEP380-303 OLE study med start date and the event record does not exist in SEP380-301 database§, then SEP380-303 AE.

\*The distinction between SEP380-301 pre-treatment event and SEP380-301 AE should be performed as specified in the SEP380-301 SAP.

§Based on a comparison of subject ID, PT, AE start date (and time if available), severity, and seriousness.

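### The SAP's match key for carried-over lead-in AEs includes severity and seriousness, so a re-entered AE that changed and has an ambiguous start date can be counted as an open-label AE

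*Protocol*

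**What the plan says.** Protocol 11.4.1 has AEs that are ongoing at the end of the lead-in study entered again in the extension eCRF, and then states: "All changes in adverse events or new adverse events occurring during the study up to the Follow-up Visit will be recorded". Protocol 12.3 lists what is assessed for an AE: "Each AE is to be evaluated for duration, severity, frequency, seriousness, action taken with the study treatment, outcome", and causality.

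SAP 18.1 defines an extension AE by its onset, at or after the first open-label extension (OLE) dose. Of the re-entered lead-in events it says: "These events will not be included in any AE summary table of SEP380-303". They go to a separate listing.

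To recognise those events, the SAP compares records across the two databases:

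- SAP 18.1, for events starting on the day of the first OLE dose when no time is available: "based on a comparison of subject ID, verbatim term, AE start date (and time if available), severity, and seriousness".
- SAP Appendix 2, Step 1, for events with a partial or missing start date: shared events "will be identified based on a comparison of subject ID, PT, AE start date (and time if available), severity, and seriousness". The footnote to Step 4 repeats this key.

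Step 4 then settles the tie: "If event start date = SEP380-303 OLE study med start date and the event record does not exist in SEP380-301 database", the event is an SEP380-303 AE.

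**The concern.** A key that links two records of one event should rest on attributes that stay fixed. Severity and seriousness are assessed again as an AE is followed. A lead-in AE that worsens, eases or becomes serious after rollover, and whose re-entered row is edited to show it, no longer agrees with its own lead-in record. The rule can then treat it as new.

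The incidence of AEs and of SAEs is a primary endpoint in SAP 3.2.1. A misassigned event would appear as an open-label AE with onset on Day 1, at its changed severity or seriousness. In PBO-SEP, it would be an event that began on placebo and is shown as starting on drug.

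Separately, 18.1 compares the verbatim term and Appendix 2 the preferred term. For the same first-dose-day tie, the two sections can give different answers.

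**Working it through.** The plan gives no figure for this rule, so there is none to reproduce. The check follows one record through Appendix 2.

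**Path of a record.** Take a true lead-in AE, ongoing at rollover, with no end date before the first OLE dose. Its severity or seriousness was changed in place, so Step 1 finds no match.

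| Start date as recorded | Caught by Step 2? | Date used | Assigned to |
|---|---|---|---|
| Day missing, month before the OLE-start month | Yes | lead-in rules | SEP380-301 |
| Day missing, same month as OLE start | No | first OLE dose | SEP380-303 |
| Only year known, earlier year | Yes | lead-in rules | SEP380-301 |
| Only year known, same year | No | first OLE dose | SEP380-303 |
| Fully missing | No | first OLE dose | SEP380-303 |
| Full date before first OLE dose | not needed | as recorded | SEP380-301 |

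Step 2 diverts only events that the known date parts place clearly before the first OLE dose. Step 3 imputes the earlier of the OLE start and the AE end date. Step 4 looks again for a match, finds none and assigns the event to SEP380-303.

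Example, with the first OLE dose on 20 May. If only the day is missing, an onset on 25 April stays in SEP380-301 and an onset on 10 May moves to SEP380-303. If only the year is known, both move.

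**Share of failed matches that are misassigned.** The documents give no onset or dosing dates. Assumptions: onset is uniform over the 42 lead-in days, and the first OLE dose is equally likely on each day of a 365-day year.

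- *Day missing.* If the first OLE dose falls on day d of a month, d − 1 of the 42 onset days lie in that month. Over the year the d − 1 values sum to 7 × 465 + 4 × 435 + 378 = 5,373. The share is 5,373 / (365 × 42) = 5,373 / 15,330 = 35%. The range is 0% (d = 1) to 30/42 = 71% (d = 31).
- *Only year known.* On day k of the year, the smaller of k − 1 and 42 onset days lie in that year. The sum is 861 + 323 × 42 = 14,427. The share is 14,427 / 15,330 = 94%, with range 0% to 100%.
- *Fully missing.* 100%.

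If the match does not depend on severity and seriousness, the same record matches at Step 1, and the share is 0% in all three cases.

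**Effect on an incidence.** SAP 4.4 gives 64 enrolled. One extra subject adds 1/64 = 1.6 percentage points in ALL EXT, if all 64 are in the Safety Population. The size of PBO-SEP is not given. At an assumed 16, 21 or 32 subjects (a quarter, about a third or half of 64), one extra subject adds 1/16 = 6.3, 1/21 = 4.8 or 1/32 = 3.1 points.

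**The case against.** Several limits are real, and they mark off stronger readings that a reader might infer.

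- *The protocol updates severity and seriousness on the re-entered row.* It does not say so. Section 11.4.1 records changes without naming attributes or saying whether a row is overwritten. Section 12.1.1 notes: "AEs may include the onset of new illness and the exacerbation of pre-existing conditions". If a worsening is entered as its own AE, the carried-over row still matches, and the new row is properly an open-label event.
- *Every changed lead-in AE with a partial date is miscounted.* Step 2 prevents this. Under the assumptions above, about 65% of day-missing cases stay in SEP380-301. Full dates before the first OLE dose are sorted by date alone.
- *Full dates on the first-dose day are a further large source.* On the planned schedule Visit 6 is Day -1 and dosing starts the next day, so an AE ongoing at Visit 6 cannot have begun on Day 1.
- *Each event adds a subject.* SAP 18.1 counts a subject once per category, so an event adds nothing where the subject already has one.

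It can also be argued that the present key errs on the safe side, by counting events that worsened on open-label drug. That does not stand. The SAP defines extension AEs by onset, and a worsened lead-in AE with a full date is already left out. The result turns on how complete the date is, which no stated rule intends.

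The best objection is to the remedy. If severity and seriousness are simply dropped, a genuine new open-label AE with the same preferred term and the same partial or missing date as a lead-in event could match it and leave every AE table. This stands, and it shapes the fix.

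The SAP also plans a listing of lead-in events found in the extension database, and a pre-lock data review. Both are useful places for a check, but neither promises this one.

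**Conclusion.** The point holds in a limited form. A carried-over AE is misassigned, against the SAP's own exclusion in 18.1, when three things coincide: its severity or seriousness changed after rollover, the change was made in the re-entered row, and its start date does not exclude onset on or after the first OLE dose. The third condition means the day is missing in the OLE-start month, only the OLE-start year is known, or the date is fully missing, with no earlier end date.

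The number of such events cannot be found from the documents and is probably small. The analysis is descriptive, so no test is affected. The most that one event can do is add 1.6 points in ALL EXT, or more in PBO-SEP depending on its size. The shares above rest on uniform onset and are only a guide.

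The conflict between verbatim term and preferred term needs no assumption about data entry and should be reconciled in any case.

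**What to change.** Use one key in SAP 18.1 and in Appendix 2, Steps 1 and 4. The best choice is a carried-over-AE flag or the lead-in AE identifier. If neither was collected, use subject ID, preferred term and start date as recorded, with partial dates compared as entered. Leave out severity, seriousness and verbatim term.

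Before database lock, review by hand:

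- every lead-in AE ongoing at rollover that has no match in the extension database;
- every match that rests on a partial or missing date, or in which severity or seriousness differs.

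The second check protects genuine new open-label events from being removed. If the sponsor wants worsening of a carried-over AE to count, the SAP should state that as a rule, so that it does not depend on date completeness.

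The cost is a short edit in two places, one pre-lock listing and a few manual checks.
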